The following informed consents are included in this study:

- Main study consent, which also includes:
 - A subsection that requires a separate signature for the 'Optional Consent for Additional Research' to allow future research on data/samples collected during this study
 - As applicable, Pregnancy Outcomes Reporting Consent for female participants who took study treatment

Women of child bearing potential must be informed that taking the study treatment may involve unknown risks to the fetus if pregnancy were to occur during the study and agree that in order to participate in the study they must adhere to the contraception requirements.

A copy of the approved version of all consent forms must be provided to Novartis after IRB/IEC approval.

Participants might be asked to complete an optional questionnaire to provide feedback on their clinical trial experience.

As per [Section 4.6](#), during a Public Health Emergency as declared by local or regional authorities i.e. pandemic, epidemic or natural disaster, that may challenge the ability to obtain a standard written informed consent due to limits that prevent an on-site visit, Investigator may conduct the informed consent discussion remotely (e.g. telephone, videoconference) if allowable by a local health authority.

Guidance issued by local regulatory bodies on this aspect prevail and must be implemented and appropriately documented (e.g. the presence of an impartial witness, sign/dating separate ICFs by trial participant and person obtaining informed consent etc.).

8 Visit schedule and assessments

The Assessment Schedule ([Table 8-1](#) and [Table 8-2](#)) lists all of the assessments and indicates with "X" or "S" when they are performed. The "X" in the table denotes the assessments to be recorded in the clinical database or received electronically from a vendor. The "S" in the table denotes the assessments that are only in the participant's source documentation and do not need to be recorded in the clinical database. All data obtained from these assessments must be supported in the participant's source documentation.

Participants should be seen for all visits/assessments as outlined in the assessment schedule ([Table 8-1](#) and [Table 8-2](#)) or as close to the designated day/time as possible, with an allowed "injection window" as described in [Section 6.3.2](#). Missed or rescheduled visits should not lead to automatic discontinuation. In the study, one month is defined as 28 calendar days.

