For all scheduled visits, any AE or SAE reported by the participant will be recorded according to [Section 10.1.1](#) and [Section 10.1.2](#). For women of childbearing potential, urine or serum pregnancy test is required prior to each administration of study drug, and drug administration can only be conducted with negative pregnancy test result (refer to [Section 8.4.3](#)).

EOS visit is mandatory for all participants. The EOS visit is conducted at the end of the Treatment period (i.e. M12), or when participants prematurely discontinue study treatment before M12, whether they plan to enter Post-treatment Follow-up period or withdraw from the study. Participants who prematurely discontinue study treatment will have their EOS visit as soon as possible. At the EOS visit, AEs and concomitant medications not previously reported must be recorded on the eCRFs.

Participant diaries

During the study, participants will be asked to complete a diary from BL/W0 onwards till EOS to record information pertinent to study treatment administration (including date and time of s.c. injections), home pregnancy testing (date and results) for women of childbearing potential and other information (e.g. AEs). The participant is requested to bring the completed diaries with them to each visit and the Investigator/Study Coordinator/Nurse must review these for completeness and for potential AEs, injection-related reactions, study treatment interruptions etc. and record information obtained from the diaries into the relevant eCRFs.

Telephone or virtual interviews

Site personnel will conduct a structured telephone interview (script provided) for W1 and W2 initial doses, and then every month in between the scheduled site visits following the W4 site visit ([Table 8-1](#) and [Table 8-2](#)). During the Treatment period, the interview should take place around time of the monthly s.c. self/home-injections to query about any new or worsening symptoms warranting an unscheduled visit, compliance with study treatment, changes in concomitant medication, injection reactions, results of home pregnancy testing and compliance with contraception requirements when applicable. During the Post-treatment Follow-up period, the interview should take place regularly every month between scheduled visits to query about any new or worsening symptoms warranting an unscheduled visit, changes in MS treatment and concomitant medication, compliance with contraception requirements and potential AEs etc.

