Participants, except for those who will continue with commercially available ofatumumab treatment, will enter the 6-month Post-treatment Follow-up period after EOS as described in [Table 8-2](#).

As per [Section 4.6](#), during a Public Health Emergency as declared by local or regional authorities i.e. pandemic, epidemic or natural disaster that limits or prevents on-site study visits, alternative methods of providing continuing care may be implemented by the investigator as the situation dictates. If allowable by a local health authority and depending on operational capabilities, phone calls, virtual contacts (e.g. tele consult) or visits by site staff/home nursing staff to the participant's home, can replace on-site study visits, for the duration of the disruption until it is safe for the participant to visit the site again.

Table 8-1 Assessment Schedule, Screening and treatment

Period	Screening	Treatment							Treatment	
Visit Name	Screening	BL/W0	W1 (Phone Interview)	W2 (Phone Interview)	W4	M3	M6	M9	M12/EOS	Unscheduled Visit ¹
Days	-30 to -1	-	7	14	28	84	168	252	336	-
Informed consent	X									
Demography, Height	X									
Inclusion / Exclusion criteria	X	X ²								
Medical history/current medical conditions	X									
MS History/Treatments	X									
COVID-19 vaccination status	X	X ³	X	X	X	X	X	X		
Physical Examination	S	S ³			S		S		S	S
Weight, Vital Signs	X	X ⁴			X	X	X	X	X	X
Electrocardiogram (ECG)	X									
Hematology	X ⁵				X	X	X	X	X	
Clinical Chemistry	X ⁵				X	X	X	X	X	
Urinalysis	X ⁵				X		X		X	
Serological markers for hepatitis B ⁶	X ⁵									
HIV antibody screen ⁷	X ⁵									
Syphilis screen ⁷	X ⁵									
Tuberculosis screen ⁷	X ⁵									
Pregnancy and assessments of fertility ⁸	X ⁵	X ³			X	X	X	X	X	
Contraception Status ⁹	X	X ³	X	X	X	X	X	X	X	
MS relapse	X	X ³	X	X	X	X	X	X	X	X
MRI	X					X			X ¹⁰	

Period	Treatment										Treatment
	Screening	BL/W0	W1 (Phone Interview)	W2 (Phone Interview)	W4	M3	M6	M9	M12/EOS	Unscheduled Visit ¹	
Visit Name	Screening										
Days	-30 to -1	-	7	14	28	84	168	252	336	-	
Adverse Events	X	X ³	X	X	X	X	X	X	X	X	
Prior/Concomitant Medications ¹¹	X	X ³	X	X	X	X	X	X	X	X	
Surgical/medical procedures	X	X ³	X	X	X	X	X	X	X	X	
Sample for B-cells ¹²	X	X ³			X	X	X		X		
Sample for IgG and IgM ¹²	X						X		X		
Drug dispensation		S			S	S	S	S			
Drug administration ¹³		X	X	X	Monthly, except for M12/EOS						
Participant diaries ¹⁴					X						
Participant Diary Review					X	X	X	X	X		

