Phone interview/virtual visit ^{15,16}			X	X	Monthly between scheduled visits						
Treatment Phase Completion									X		

¹ Assessment to be recorded in the clinical database or received electronically from a vendor

² Assessment to be recorded in the source documentation only

³ Unscheduled visit: assessments performed as unscheduled visits will depend on the clinical needs of the participant. All participants with neurological symptoms suggestive of an MS relapse should at least have the mentioned assessments in table 8-1 performed. Other assessments may be done as appropriate.

⁴ Inclusion/exclusion criteria need to be checked again before first dose of study drug.

⁵ Assessments to be completed prior to first study drug administration.

⁶ Vital signs should be obtained 30-60 min before sc injection (if premedication is administered, pre-injection vital signs should be obtained before premedication is administered).

⁷ Laboratory results must be available prior to Baseline/Week 0 (BL/W0) to evaluate the Inclusion/Exclusion criteria.

⁸ Hepatitis B screening is required in all study participants, including hepatitis B surface antigen (HBsAg) and hepatitis B core antibody (HBcAb) testing. These can be complemented with other appropriate markers as per local guidelines. For detailed guidance, refer to [Section 16.4.2](#).

⁹ HIV, Syphilis and Tuberculosis testing must be done at central lab as part of eligibility check (Exclusion criterion #6 and #9) for all participants.

¹⁰ Women of childbearing potential only -For Screening and EOS visits, serum pregnancy test will be conducted in central lab. Monthly urine pregnancy tests will be conducted between scheduled visits(starting after W4) at home or at site prior to the administration of study treatment. In case of a positive test result, the participant must contact the investigator immediately and confirmatory testing should be performed at the investigator's discretion.

¹¹ Contraception MUST be used during the study treatment period and for at least 6 months after the last dose of study drug. Participant's contraception status must be reviewed and documented to ensure method of contraception continues to be appropriate per protocol requirement for effective contraception.

Period	Screening	Treatment								Treatment
		BL/W0	W1 (Phone Interview)	W2 (Phone Interview)	W4	M3	M6	M9	M12/EOS	
Visit Name	Screening	-	7	14	28	84	168	252	336	Unscheduled Visit ¹
Days	-30 to -1	-	7	14	28	84	168	252	336	-

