¹⁰ MRI scan at the End of Study (EOS) is needed if there was no MRI scan in the last 3 months.

¹¹ Including corticosteroids used to treat MS relapse; any newly started MS treatment as applicable (for participants who have discontinued study medication).

¹² The assessments (samples taken for IgG and IgM, B-cells) should be completed prior to study drug administration.

¹³ The first s.c. injection at W0 will be administered [REDACTED]

¹⁴ Study treatment administration (including date and time of s.c. injections) and home pregnancy testing (date and results) for women of childbearing potential will be recorded for each home injection. Other information (e.g. AEs) will be recorded continuously.

¹⁵ Phone interview will be performed by site staff for W1 and W2, and then every month starting from W4 between scheduled visits. The interview should take place around time of the monthly s.c. self/home injection to query about any new or worsening symptoms warranting an unscheduled visit, injection reactions, results of home pregnancy testing and compliance with contraception requirements.

¹⁶ Phone interview/virtual visits are also applicable to the scheduled visits for participants who exceptionally cannot come to the study site for a face-to-face examination due to a Public Health Emergency (e.g. restricting the subject's general access to sites).

Table 8-2 Assessment Schedule, Post-Treatment Follow-up

Period	Post-Treatment Follow-Up		
Visit Name	V1 ¹	End of FU ^{1,2}	Unscheduled Visit ³
Days	EOS+3 months	EOS+6 months	NA
Weight, Vital Signs	X	X	X
COVID-19 vaccination status	X	X	
Physical Examination	S	S	S
Clinical Chemistry	X	X	
Hematology	X	X	
Urinalysis	X	X	
Pregnancy Test (serum) ⁴	X	X	
Contraception Status ⁵	X	X	
Sample for B-cells	X	X	
Sample for IgG and IgM	X	X	
MS relapse	X	X	X
MRI		X ⁶	
Concomitant medications ⁷	X	X	X
Surgical/medical procedures	X	X	X
Adverse Events	X	X	X
Phone interview/virtual visit ^{8,9}	Monthly between scheduled visits		
Post Treatment Part Completion		X	

^X Assessment to be recorded in the clinical database or received electronically from a vendor

^S Assessment to be recorded in the source documentation only

¹ Visits 1 and end of FU are applicable to all participants, except for completers of the Treatment period who decide to continue with commercially available ofatumumab treatment.

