Hepatitis markers	HBV screening is required in all participants, including Hepatitis B surface antigen (HBsAg) and hepatitis B core antibody (HBcAb) testing. Participants with positive hepatitis B serology (either HBsAg or HBcAb) should consult a liver disease expert before the start of treatment and should be monitored and managed following local medical standards to prevent HBV infection or reactivation. NOTE: If the infectious disease expert finds no evidence of acute or chronic hepatitis infection and considers the serology results false positive and not clinically relevant, the Investigator must document that the serology results are considered false positive and may then enroll the participant.
Pregnancy Test ¹ (women of childbearing potential)	Serum / Urine pregnancy test (refer to Section 8.4.3)
Additional tests ²	HIV antibodies, syphilis and TB screening test. Serology markers for other hepatitis, as appropriate; Follicle Stimulating Hormone (FSH) (for female participants with unclear fertility status). Cerebrospinal fluid (CSF) aliquot in the event of suspected CNS infection (PML)

¹ Serum pregnancy test analyzed in Central lab is required for Screening, EOS visits and for scheduled visits during Post-treatment Follow-up period. For the other scheduled visits, urine pregnancy test is to be analyzed with pregnancy kits provided by the central lab; monthly urine pregnancy test is to be conducted with pregnancy kits prior to every study drug administration. Urine pregnancy tests by local lab at site can be considered if pregnancy kit is not allowed per site requirement.

² HIV, syphilis and tuberculosis testing must be done as part of eligibility check (Exclusion criterion #6 and #9) for all participants. These screening tests should be done by the central lab.

8.4.2 **Electrocardiogram (ECG)**

An ECG will be obtained and reviewed locally for the eligibility assessment at Screening. Additional unscheduled ECGs may be performed at Investigator's discretion if clinically indicated.

ECGs must be recorded after 10 minutes rest in the supine position to ensure a stable baseline/according to the ECG investigator manual. In the case of a series of assessments, ECG should be the first assessment obtained while the participant is at rest (refer to [Figure 8-1](#)).

Figure 8-1 Timing of study procedures

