8.4.3 Pregnancy and assessments of fertility

All pre-menopausal women who are not surgically sterile will have pregnancy testing. Additional pregnancy testing might be performed if requested by local requirements.

Serum pregnancy tests will be conducted by central lab at Screening, EOS visit and the scheduled visits in the Post-treatment Follow-up period. Urine pregnancy tests will be conducted for all women of childbearing potential at all the remaining scheduled visits and monthly starting after W4 between the scheduled visits (with urine pregnancy testing kits provided by the central lab unless not permitted per site requirement) prior to study drug administration. The participants will document the date and results of each home pregnancy test in a diary provided for the study. A monthly site contact (refer to [Table 8-1](#)) will also be conducted with the participants, which includes questions to confirm that the home urine pregnancy testing is done and the result is correctly documented. In case of a positive test result, the participant must contact the Investigator immediately for confirmatory testing at the Investigator's discretion. It is important that participants are instructed to perform the urine pregnancy test first and only if the test result is negative then proceed with the administration of the study treatment. The communication process described above as part of the monthly site contacts with the participant should be followed so that the site is informed and can verify the pregnancy test results.

If participants cannot visit the site to have serum pregnancy tests during a Public Health emergency as declared by Local or Regional authorities i.e. pandemic, epidemic or natural disaster, that limits or prevents on-site study visits, urine pregnancy test kits may be used. Relevant participants can perform the urine pregnancy test at home and report the result to the site. It is important that participants are instructed to perform the urine pregnancy test first and only if the test result is negative proceed with the administration of the study treatment. A communication process should be established with the participant so that the Site is informed and can verify the pregnancy test results (e.g., following country specific measures).

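### Section 8 requires a negative pregnancy test before every dose, but Table 8-1 and its pregnancy footnote schedule none for the Week 1 and Week 2 doses

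*Protocol*

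**What the plan says.** **The rule.** Protocol Section 8 (Visit schedule and assessments) says that for women of childbearing potential a "urine or serum pregnancy test is required prior to each administration of study drug". Dosing may go ahead only on a negative result, and no dose is exempted. The sentence refers to Section 8.4.3 for detail.

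**The schedule.** Section 8 also says that the assessment schedule "lists all of the assessments and indicates with" a mark when each one is performed. In Table 8-1, drug administration is marked at W0, W1 and W2 and monthly after that, except at M12/EOS. The row "Pregnancy and assessments of fertility" is marked at Screening, BL/W0, W4, M3, M6, M9 and M12/EOS, and is blank at W1 and W2. The pregnancy footnote to the table adds: "Monthly urine pregnancy tests will be conducted between scheduled visits(starting after W4) at home or at site".

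**The detail.** Section 8.4.3 assigns serum tests to Screening, EOS and follow-up, and then says: "Urine pregnancy tests will be conducted for all women of childbearing potential at all the remaining scheduled visits and monthly starting after W4". Participants are told to test first and inject only if the test is negative. Table 8-4 footnote 1 says "For the other scheduled visits, urine pregnancy test is to be analyzed with pregnancy kits provided by the central lab" and, in the next clause, "monthly urine pregnancy test is to be conducted with pregnancy kits prior to every study drug administration".

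**Recording.** Table 8-1 footnote 14 says that "home pregnancy testing (date and results) for women of childbearing potential will be recorded for each home injection". The diary starts at BL/W0. Footnote 15 places telephone interviews at W1 and W2 and lists home test results among the queries, although its sentence on timing refers to the monthly injection.

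**The concern.** The test is a condition that the protocol itself sets for each dose. Sites usually work from the assessment table, and that table shows two doses with no test beside them. A site that follows Table 8-1 and its pregnancy footnote to the letter could give the W1 and W2 doses untested and so breach Section 8. A site that follows Section 8 needs tests, and kits in participants' hands, that the table does not provide for.

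Two things are at stake. One is a small part of the pregnancy safeguard during the initial dosing. The other is consistency between sites: the SAP (Section 2.3.1) summarises protocol deviations for the FAS, so the sponsor would have to decide whether an untested W1 or W2 dose counts as one.

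**Working it through.** The plan gives no figure to reproduce here. The check is a count of doses against scheduled tests, followed by a comparison of the texts.

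**Planned doses** (Section 6.3.2 and Table 8-1; a month is 28 days). W0, W1 and W2 give 3. W4 (which is M1) through M11 gives 11, because there is no dose at M12/EOS. Total: 3 + 11 = 14.

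**Scheduled pre-dose tests** (Table 8-1 and its pregnancy footnote):

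| Doses | Number | Source of the test |
|---|---|---|
| W0, W4, M3, M6, M9 | 5 | Marked in the pregnancy row |
| M2, M4, M5, M7, M8, M10, M11 | 7 | Footnote: monthly between visits, after W4 |
| W1, W2 | 2 | None |

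Covered: 5 + 7 = 12 of 14. Not covered: 14 − 12 = 2, and 2/14 = 14.3%. Section 8 requires 14 of 14.

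**Are the blanks real?** The contraception row directly below is marked at W1 and W2, so a column shift in the text is not a likely explanation.

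**Does Section 8.4.3 fill the gap?** That depends on whether W1 and W2 count as scheduled visits.
- If they do, Section 8.4.3 and Table 8-4 footnote 1 ask for a urine test at both, and 0 of 14 doses lack one. The blank cells in Table 8-1 are then an omission.
- If they are only telephone contacts, 2 of 14 doses lack one, and Section 8.4.3 falls short of Section 8.

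Neither text names W1 or W2. Footnote 16 says that phone interviews can also be applied to scheduled visits, which suggests that the two are different things. On either reading, some text needs an edit.

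**Age of the last scheduled test.** Taking the W0 test as done on the day of the first dose, it is 7 days old at W1 (Day 7) and 14 days old at W2 (Day 14). The interval between later tests is 28 days.

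**The case against.** The strongest reply is that an empty cell does not release a site from an explicit dosing condition. Section 8 is categorical. Table 8-4 footnote 1 repeats the requirement for every administration, Section 8.4.3 says to test first, and footnote 14 expects a test result for each home injection. All of this points to testing before every dose. This part stands, and it fixes the nature of the problem. A reader might infer that the protocol permits untested dosing at W1 and W2, or that it contains two rival rules. The documents support neither reading. They show one rule and a schedule that does not fully carry it out.

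It can also be said that the phrase about starting after W4 qualifies only the monthly between-visit tests and does not exempt the weekly doses. That is correct, but it also means that the footnote gives W1 and W2 no test.

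A third argument is that W1 and W2 are scheduled visits. They have named columns and assigned days, Section 8 speaks of later calls between scheduled site visits, and the glossary defines a tele-visit. This reading is plausible. If it is right, Section 8.4.3 already requires the tests, but the table that is said to list all assessments still omits them.

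Fourth, seven of the twelve covered tests have no cell in the pregnancy row either. True, but those months have no column and the footnote provides for them. W1 and W2 have columns and are left blank, and the footnote does not mention them.

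Finally, the interview script, the laboratory manual and some redacted text on where injections are given were not available. They may guide sites, so actual confusion at sites is not shown. They do not change the blank cells or the footnote.

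**Conclusion.** The point holds as an incomplete schedule. Table 8-1 and its pregnancy footnote provide a pre-dose test for 12 of 14 planned doses and none for W1 and W2, while Section 8 requires one for each. Section 8.4.3 does not name these doses and so does not clearly close the gap. The count assumes full dosing through M11 and takes the table and footnote as written. If W1 and W2 are read as scheduled visits, the text of Section 8.4.3 covers them and only the table is at fault.

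Severity is minor. The W0 test is 7 and 14 days old at these doses, which is fresher than the 28-day spacing used later. Contraception status is reviewed at both calls. The primary and secondary efficacy analyses are unaffected. The case for acting is that a site working from the schedule could breach a stated safeguard, and that the correction is cheap.

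**What to change.** Bring the schedule up to the rule:

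- mark a urine test at W1 and W2 in the pregnancy row of Table 8-1;
- name W1 and W2 in the pregnancy footnote to that table and in Section 8.4.3;
- supply the two kits at BL/W0, where Table 8-1 already marks drug dispensing, the next being at W4;
- state that the existing W1 and W2 calls confirm that the test was done and was negative.

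All 14 planned doses would then have a scheduled test.

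The cost is a few short text edits and two extra urine kits per woman of childbearing potential. The documents do not give the number of such women. If all of the approximately 100 participants were in that group, the upper bound is 2 × 100 = 200 kits, of a type already supplied through the central laboratory. No new visit or call is needed.

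Relaxing the Section 8 rule to exempt W1 and W2 would also remove the mismatch, but it is not recommended. It would take away a stated safeguard, and nothing in the documents suggests that the sponsor wants that.
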